The study has a number of aims and the power analysis is provided separately for each aim: (1) In order to examine the age related ability to use the BARF scale we will recruit 28 subjects each in the ages of 3, 4, 5, 6, 7, 8, 9, 10, 11, 12 and >12 years years (28 X 11 = 308). Power analysis was based on an alpha of 0.05, power of 80% and a large effect size (Cohen's d = 0.80) as it was assumed a large difference would be needed for the results to have clinical utility (Pain 2011; 152: 1327-33). This suggested a group size of 24 would be needed. Allowing for a drop out rate of 20% we plan to recruit 28 in each of the 11 groups. (2) Power analysis for minimum clinically relevant difference in BARF scores: A one face difference in the BARF scale is the minimum difference that can be detected. A previous study showed that the mean BARF scores in the postoperative period in children was 1.6 +/- 2.4 (Pediatrics. 2011 Jun;127(6):e1542-9) . In order to detect a 1 face difference with 80% power at the 0.05 level of significance we will need 93 subjects who had a change in their nausea scores. Assuming an incidence of postoperative nausea and vomiting (PONV) of 33% (which is similar to previous data in children), a group size of 93 X3= 279 will be required to obtain 93 subjects with a change in nausea scores. We plan to recruit 387 subjects to allow for a 35% dropout rate.

This sample size will have a >80% power for the other aims of the study (The BARF and VAS scores associated with a patient's perception of the need for treatment and the test - retest reliability of the VAS and BARF scores when nausea is rated as unchanged.)

G2. Data Analysis

Provide a description of your plan for data analysis. State the types of comparisons you plan (e.g. comparison of means, comparison of proportions, regressions, analysis of variance). Which is the PRIMARY comparison/analysis? How will the analyses proposed relate to the primary purposes of your study?

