Statistical Analysis: (1) The mean and SD of all scores will be calculated along with their distribution. The incidence of postoperative nausea and postoperative vomiting in the PACU and after discharge (post-discharge nausea) will be calculated. The incidence of severe nausea (score>6 on the BARF scale) and severe vomiting (3 or more episodes over 24 hours) will also be determined. (2) We will record the age of a child and their ability to rate their nausea on the BARF and VAS scales to determine the minimum age where a patient can reliably use the scale. (3) Changes in BARF and VAS nausea scores will be calculated for subjects who report their nausea as a little worse than before or a little better than before, to determine the minimum change in scores of clinical relevance. (4) The BARF score and its relationship to the request for rescue antiemetics will be examined by a Spearman's rank correlation. (5) The relationship between the first and subsequent BARF and VAS nausea scores in patients who state their nausea is 'the same as before?' will be examined by a Spearman's rank correlation and a Cronbach's alpha calculation. This will provide the test ? retest reliability.

Section H: Potential Risks/Discomforts

Describe and assess any potential risks/discomforts; (physical, psychological, social, legal, or other) and assess the likelihood and seriousness of such risks:

The risks are limited to possible loss of confidentiality as there are no changes in surgical or anesthetic management of the child other than obtaining data on estimating the degree of nausea. Loss of confidentiality is unlikely in view of standard steps taken to avoid this.

Section I: Potential Benefits

Describe potential benefit(s) to be gained by the individual subject as a result of participating in the planned work.

Subjects will not have any direct immediate benefits from participating in these studies.

Describe potential benefit(s) to society of the planned work.

Determining the clinical utility of a faces pain scale will facilitate treatment and research into this clinically important realm of suffering for children of all ages. Future patients may benefit from having such a tool as it will permit clinicians to measure the symptom severity and then treat such patients

Do anticipated benefits outweigh potential risks? Discuss the risk-to-benefit ratio.

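### The >80% power claimed for the treatment-need and test-retest aims has no stated basis, and the planned reliability coefficients are likely to be driven by pairs of zero scores

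*Combined protocol and SAP*

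**What the plan says.** Section G1 opens by stating that "the power analysis is provided separately for each aim". It then gives two calculations, one for the age groups and one for the minimum relevant difference. The second rests on a report that "the mean BARF scores in the postoperative period in children was 1.6 +/- 2.4" and concludes: "In order to detect a 1 face difference with 80% power at the 0.05 level of significance we will need 93 subjects". To find those children it continues "Assuming an incidence of postoperative nausea and vomiting (PONV) of 33" per cent, so that "a group size of 93 X3= 279 will be required to obtain 93 subjects with a change in nausea scores". The total follows: "We plan to recruit 387 subjects to allow for a 35% dropout rate".

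The two remaining aims, the scores at which a child perceives a need for treatment and test-retest reliability, share one closing sentence: "This sample size will have a >80% power for the other aims of the study".

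G2 item (4) plans a Spearman correlation between BARF score and request for rescue antiemetics. G2 item (5) plans Spearman and Cronbach's alpha for reliability: "The relationship between the first and subsequent BARF and VAS nausea scores in patients who state their nausea is" unchanged. That set is defined by the child's own answer on the five-point Likert item in F2. Inclusion criterion (4) in F1 requires 24 hours without nausea or vomiting before entry.

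**The concern.** A reader of G1 would take both aims to be adequately powered, yet nothing in the text allows that to be checked. Neither aim has a null value, a target value or an expected number of analysable children.

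The reliability aim has a second difficulty. The sizing argument treats having PONV as the same thing as having a change in score. The other two-thirds are then, for the most part, children who were never nauseated and who score 0 each time. If they make up most of the unchanged group, a correlation over the whole group mainly records that children without nausea score 0 twice and children with nausea score something twice. It says little about whether a nauseated child gives the same score again, which is what test-retest reliability of an intensity scale should show. The study could report excellent reliability that comes from the zeros.

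For treatment need, Section D asks which scores go with a perceived need. That is an estimate, and its precision depends in large part on how many children ask for treatment. G1 does not give that number.

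**Working it through.** **1. The plan's own figures.** The >80% has no inputs, so there is nothing to reproduce. By contrast, the 93 in G1 item (2) can be approached: 2 × 2.4² × (1.96 + 0.84)² / 1² gives 91 per group (92 with the t distribution), assuming a two-sided 5% level and the two-group formula.

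**2. Expected numbers, from G1.**
- Analysable after 35% loss: 387 × 0.65 = 251.55, about 251.
- With a change, at one-third: 83.85, about 84.
- Without a change: 167.70, about 168.

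If all 279 were analysable, the last figure would be 279 × 2/3 = 186.

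**3. What >80% could mean against rho = 0.** With Fisher's z, the Spearman variance 1.06/(n − 3), a two-sided 5% level and 80% power, the detectable rho is tanh[(1.96 + 0.84) × √(1.06/(n − 3))].
- n = 251: 0.18.
- n = 168: 0.22.

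So the claim is easily true for this null, but a correlation of that size would not be called reliability.

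**4. What it could mean against a reliability benchmark.** The documents give no benchmark, so these are assumptions. Power = Φ[(atanh ρ₁ − atanh ρ₀)/√(1.06/(n − 3)) − 1.96] at n = 168, supposing every pair is informative:

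| Null | True value | Power |
|---|---|---|
| 0.70 | 0.80 | 82% |
| 0.70 | 0.75 | 26% |
| 0.80 | 0.85 | 50% |

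The answer depends entirely on a hypothesis that G1 does not state.

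**5. Is a mostly-zero group plausible?** Suppose two-thirds score 0. From the mean of 1.6 and SD of 2.4 in G1, the nauseated third would have mean 1.6 × 3 = 4.8 and variance 3 × (2.4² + 1.6²) − 4.8² = 24.96 − 23.04 = 1.92, an SD of 1.4. These values are possible, so the plan's inputs are consistent with two-thirds zeros. They do not prove it.

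**6. What the planned coefficients would then show.** Take 168 unchanged pairs. Assume 8 or 17 (about 5% or 10%) come from persistently nauseated children, and that their two scores are drawn independently and uniformly from 2, 4, 6, 8 and 10. All others score 0/0. Repeatability among the nauseated is therefore nil by construction.

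For alpha, the non-zero scores have mean 6 and variance 8. With p the nauseated share, the all-pairs Pearson correlation is r = 36(1 − p)/(44 − 36p), and alpha = 2r/(1 + r).
- p = 8/168: r = 0.81, alpha = 0.90.
- p = 17/168: r = 0.80, alpha = 0.89.

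Simulation gives the same alpha, a Spearman above 0.99 over all pairs, and a Spearman of about 0 within the nauseated children. The spacing of the faces does not matter, since both coefficients are unaffected by rescaling. If every pair were 0/0, both coefficients would be undefined.

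**The case against.** Three objections carry weight.

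First, a reader might infer from G1 that the unchanged group is nausea-free by definition and so contains no information on reliability. The documents do not support that. The 33% is a multiplier used to reach 93 children with a change. It does not define the retest set, which G2 item (5) selects on the child's answer. F2 schedules ratings on waking, around analgesic or antiemetic treatment, and before discharge, so a child with persistent nausea can answer that it is the same. One such child can be enough to make the coefficients computable. The VAS, a mark on a line, may also yield small non-zero values. This objection stands, and the point is limited to a group that is probably mostly zeros.

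Second, a reader might infer that the >80% claim is false. That is not shown either. For the Spearman test named in G2 item (4), more than 80% power against zero is plausible, and 168 informative pairs would give 82% for 0.80 against 0.70. Lower figures come from benchmarks that the plan does not contain.

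Third, restricting reliability to pairs with a non-zero score selects on the outcome. It removes agreeing zeros, keeps 0/non-zero disagreements, and so tends to understate reliability. That is correct, and it is why the restricted value should sit beside the all-pairs value and not replace it.

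None of this supplies the missing hypothesis or subgroup size, or protects the all-pairs coefficients from the zeros.

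**Conclusion.** The point holds in two parts. The >80% statement is unsupported: G1 promises a power analysis for each aim and for these two gives only an assertion, which is easily met only against a null that does not bear on reliability. The reliability analysis is also exposed to a group that is probably dominated by 0/0 pairs. In the worked case it would return a Spearman above 0.99 and an alpha of about 0.89 when nauseated children do not repeat their scores at all.

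The second part rests on three assumptions: that G1's equation of PONV with change roughly describes the data, that 8 to 17 of 168 unchanged children are persistently nauseated, and that their two scores are unrelated. The last is an extreme case, chosen to show that these coefficients cannot detect poor repeatability. It is not a prediction about the BARF scale.

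**What to change.** In G1, delete the final >80% sentence. Alternatively, replace it with the expected number of unchanged pairs with non-zero scores and the expected number of children wanting treatment, each with the resulting 95% CI width over a stated range of assumptions.

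In G2 item (5), report reliability with a 95% CI for pairs with at least one non-zero score alongside the all-pairs value, and state the number of 0/0 pairs.

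The cost is protocol wording and one added analysis, with no new subjects, ratings or procedures. The downside is that a favourable figure is withdrawn. The non-zero subset will also be small, with a wide interval and a tendency to understate reliability, so the two values need to be read together.

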Pediatric research in the management of nausea has been limited by the absence of a reliable method to quantify the intensity of this subjective symptom. In adults, the visual analog scale (VAS) is an accurate tool, but this has not been shown to be reliable in young children. By default the most common objective outcome measure used in pediatric studies has been the incidence and number of emetic episodes. This measure, however, correlates poorly with the somatic subjective symptom of nausea.

Apfel et al have shown that 30-40% of adult patients undergoing surgery have post discharge nausea and / or vomiting while 12% have vomiting. These data on nausea in adults were based on a visual analog scale for nausea. There are no data on the incidence of postoperative nausea in children since the severity of symptoms are difficult to measure as younger children are known to be unable to use the VAS reliably.

Recently a pictorial scale for measuring nausea, the Baxter Animated Retching Faces (BARF) scale, has been developed and shown to have construct, content and convergent validity as an instrument to measure nausea in children. The clinical usefulness of this scale in determining the incidence of postoperative and post-discharge nausea in children has yet to be determined including the lowest age where it can be used reliably, the score associated with a patient's perception of a need for treatment, the minimum change in the scores of clinical relevance and the test-retest reliability when nausea is rated as not having changed.

Section D: Purpose and Objectives

This study in the pediatric patient population is designed to determine: (1) The incidence of postoperative

nausea as compared to postoperative vomiting in the Post Anesthetic Care Unit (PACU) and on discharge (Post Discharge nausea and Vomiting). (2) The age related differences in the reliability and usefulness of the BARF and VAS scales for measuring nausea. (3) The minimal clinically relevant differences in nausea on the BARF and VAS scales. (4) The BARF and VAS scores associated with a patient's perception of the need for treatment. (5) The test - retest reliability of the VAS and BARF scores when nausea is rated as unchanged.

Section E: Protocol Risks/Subjects

E1. Risk Category

Category 1: Research not involving greater than minimum risk.

E2. Subjects

Gender:

Both

Age:

Adolescent (13-17 yrs), Child (3-12 yrs)

Ethnicity:

All Ethnicities

Primary Language:

English

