We will first determine if the child will qualify for the study by showing 6 cut out shapes of different sizes and asking the child to first choose the largest size, then the smallest, then the largest remaining size until no more shapes are left. If the child qualifies for the study and if they agree to participate, we will obtain baseline values as described below. Baseline Values: Baseline assessments of nausea before the procedure would be obtained from the awake child using both the visual analogue scale and the BARF scale. The order in which the first scale is presented to the patient for assessment will be randomized to reduce the potential for an order effect. The script for the scales would be standardized in keeping previous studies. For the nausea scales, the script would be: "Have you thrown up or felt like you were going to throw up before? How did your tummy feel then? We call that feeling of being sick to the stomach as nausea. VAS Scale: On this line the far left indicates "No nausea" and the far right? Worst nausea ever." Can you show me on this line how much nausea you have right now? Faces Scale: "These faces show children who feel no nausea at all, who feel a little bit nauseous, who feel even more nauseous, and these are children who have a lot of nausea." (Point to the each face at the appropriate time). Which face is more like you right now?" The evaluator will assess if the child has understood the instructions and has the ability to provide a reliable response.

Perioperative Care

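### Aim 2 asks for reliability by age, but no planned analysis estimates it, and the 80% power for d = 0.80 belongs to a comparison of age-group means that the plan never makes

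*Combined protocol and SAP*

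**What the plan says.** **Objective.** Section D, item (2) sets out to determine "The age related differences in the reliability and usefulness of the BARF and VAS scales for measuring nausea".

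**Analysis.** Section G2, item (2): "We will record the age of a child and their ability to rate their nausea on the BARF and VAS scales", in order "to determine the minimum age where a patient can reliably use the scale". Nothing more is given for this aim. G2 item (5) plans Spearman's correlation and Cronbach's alpha for first and later scores in children who report unchanged nausea. It does not mention age.

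**Sample size.** Section G1, item (1) recruits single-year groups from 3 to 12 and one pooled group above 12. "Power analysis was based on an alpha of 0.05, power of 80% and a large effect size", given as a Cohen's d of 0.80. The result is 24 per group before losses. Item (1) then covers losses as follows: "Allowing for a drop out rate of 20% we plan to recruit 28 in each of the 11 groups".

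**How ability is judged.** The only description is in Section F2, under the baseline values: "The evaluator will assess if the child has understood the instructions and has the ability to provide a reliable response". The eligibility criteria in Section F1 require children to have had no nausea or vomiting in the preceding 24 hours and to pass the seriation task. They exclude children who cannot rate how intense a symptom is.

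**The concern.** Objective, analysis and sample size concern three different quantities. The objective is reliability as a function of age. The analysis is a record of ability by age, with neither ability nor reliable use defined. The sample size is for a standardised difference between means. Followed exactly, the plan yields no estimate of reliability at any age, and its 80% power attaches to no test in G2.

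The baseline check is also weak evidence of reliable use. Every eligible child should be free of nausea at that point, so a child who always chooses the no-nausea end gives the expected answer whether or not the scale is understood.

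At stake is the minimum age at which each scale can be used. Without a stated statistic or criterion, that age could be chosen after the data are seen.

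**Working it through.** **1. The plan's own figure.** Inputs from G1 (1): alpha 0.05, power 80%, d = 0.80. Sidedness is not stated, so two-sided is assumed.

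- Normal approximation: n = 2 × ((1.960 + 0.842) / 0.80)² = 24.5, so 25 per group. The t-test gives 25.5, so 26.
- One-sided gives 20 (t-test 21), and a paired design gives 15.

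The stated 24 is within 2 of the two-sided, two-group result and well away from the others. It is a calculation for comparing the means of two age groups.

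**2. Is that comparison in G2?** Item (1) gives means, SDs and incidences. Item (2) records age and ability. Item (3) takes score changes in children who are a little better or a little worse. Item (4) relates the BARF score to requests for rescue. Item (5) is test-retest. None compares means between ages.

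**3. Power if the comparison were made.**

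- Keeping 24 after 20% loss needs 24 / (1 − 0.20) = 30. The planned 28 covers a loss of 1 − 24/28 = 14.3%.
- Remaining after 20% loss: 28 × 0.80 = 22.4, about 22.
- Normal approximation at 22 per group: 0.80 × √(22/2) − 1.960 = 0.693, which is 75.6% power. The t-test gives 73.6%.
- With no loss, 28 per group gives 83.6% (t-test).
- G1 (2) recruits 387 in all with 35% dropout. Spread evenly over the groups (an assumption), 387/11 = 35.2, and 35.2 × 0.65 = 22.9. With 20% dropout instead, 28.1 remain.

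**4. Precision of what item (2) can deliver.** Exact (Clopper-Pearson) 95% intervals for the proportion able at one age:

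| Able / assessed | Estimate | 95% interval |
|---|---|---|
| 18/22 | 82% | 60% to 95% |
| 20/22 | 91% | 71% to 99% |
| 22/22 | 100% | 85% to 100% |
| 25/28 | 89% | 72% to 98% |
| 32/35 | 91% | 77% to 98% |

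Separating two ages with assumed abilities of 90% and 70% has 38% power at 22 per group (62 per group would be needed for 80%). For an assumed 90% against 50%, power is 85%. The documents give no ability rates.

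**5. Precision of reliability in a band.** Ages 3 and 4 together have between 2 × 22.4 = 44.8 and 2 × 28 = 56 children. At the 33% incidence of postoperative nausea and vomiting assumed in G1 (2), about 15 to 18 would have symptoms, and fewer of these would report no change. As an illustration, an assumed correlation of 0.8 has an approximate 95% interval of 0.42 to 0.94 with 15 pairs and 0.52 to 0.92 with 22 (Fisher z, variance (1 + r²/2)/(n − 3)).

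**The case against.** Item (2) does not say that ability is judged only at baseline. Ratings are also taken in the PACU, around treatment and before discharge, and ability might be judged there too. That stands: the supportable criticism is that ability and reliable use are undefined, and that the one check described is weak.

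Three stronger readings are tempting, and the documents do not support them.

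- *The minimum age must rest on about 22 children per year.* The 22 is derived, not stated. If ability comes from the baseline check, later losses hardly matter and 28 per age is the better figure, or about 35 if all 387 are spread evenly. The group above 12 is not a single year. Nor does the group size follow from the missing test: these are two separate weaknesses.
- *The plan will pick the minimum age by a threshold on yes/no proportions.* No such rule is written, so its error rate cannot be charged to the plan.
- *Logistic regression on age must replace item (2).* Any advantage depends on the true curve being logistic. If ability levels off below 100%, a curve forced to rise to 100% can misplace the age. The model and its threshold are design choices.

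Reliability in unchanged pairs has its own limit: many pairs may be zero on both occasions, which is as uninformative as a nausea-free baseline. This is a reason to report the number of such pairs and the intervals. It does not justify leaving age out.

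**Conclusion.** The concern holds in this form. Aim 2 has no analysis that estimates reliability by age, and the 80% power in G1 (1) describes a comparison absent from G2. Both follow from the text and need no assumption.

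The size rests on assumptions. If age-group means were compared two-sided after 20% loss, power would be about 74%. Single-year proportions near 90% carry intervals of roughly 71% to 99% with 22 children, or 72% to 98% with 28, so the choice of denominator hardly changes the conclusion. The plan should be amended, but neither the design nor the recruitment total has to change. Any minimum age found will describe pre-screened children only, because those who fail the seriation task are not enrolled.

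**What to change.** - **Reliability by age.** Repeat the G2 (5) analysis by age band for each scale, with 95% intervals. From the postoperative ratings, also report the BARF-VAS discrepancy by band. State how many unchanged pairs are zero on both occasions.
- **Ability by age.** Define ability and reliable use in G2 (2), and report the proportion able to use each scale at each age with an exact 95% interval. Any smooth age model should be a supplement only and should allow a ceiling below 100%.
- **Sample size.** Restate G1 (1) as the precision of these estimates in place of 80% power for d = 0.80, with the denominator after losses made explicit.
- **Scope.** State that the minimum age applies to children who passed the seriation screen.

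The cost is wording and modest programming on data already collected, with no added subjects or assessments. The downside is that band-level reliability will be imprecise, most of all at the youngest ages, and the report should say so.

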After providing baseline values in the preoperative holding area, the patient's anxiety would be assessed using the validated modified Yale Preoperative Anxiety scale (mYPAS) (12), while the child is in the holding area, at the time of separation and when the face mask is applied during induction of anesthesia. The child would receive general anesthesia. The choice of drugs, techniques and perioperative management, including the need (if any) for preoperative medication, will be determined by the Attending Anesthesiologist according to the clinical needs and will not be changed for the purposes of the study. The patient will be monitored in keeping with the standards and policies of the department of Anesthesiology, Texas Children's Hospital. All Perioperative data will be collected via medical record review. In the Post Anesthetic Care Unit (PACU) patients will receive standard care, including analgesic or antiemetic therapy as prescribed by the Attending Anesthesiologist based on his opinion of the clinical needs of the situation. When awake, the patients will be asked to rate their nausea on both scales (VAS and BARF for nausea). The order of presentation of scales will be the same as in the preoperative area. If a child receives analgesic or antiemetic therapy, he/she will be asked to rate the pain and nausea immediately before receiving the drug and 30-60 minutes after receiving treatment. In summary, patients will rate their nausea using the VAS and BARF scales for nausea at these

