time points: (1) before induction of anesthesia, (2) when awake in the PACU, (3) just before, and (4) 30-60 mins after receiving analgesic or antiemetic therapy and (5) just before discharge home. The order of presentation of scales will be randomized but the same for all time points for an individual subject. After the first set of assessments are done in the PACU, patients will also be asked to rate their nausea on a 5 point Likert scale as : (1) Much worse than before, (2) A little worse than before, (3) The same as before (4) A little better than before and (5) Much better than before. They will also be asked if they want any treatment of their nausea. Another set of assessments will be just prior to discharge. All other aspects of patient management will be the standard care given to such children at the Texas Children's Hospital. Patients will be discharged from the PACU when they have achieved the standard criteria set for discharge at the TCH. At the time of discharge we will give the parents a diary to record the the MAXIMUM nausea on the VAS and BARF scales and mail it back in a stamped envelope. We will phone them about 24 hours after surgery and ask if the child had any nausea, vomiting and what medications were used after going home. We will ask the parent to rate their satisfaction with the control of nausea and with the entire perioperative experience on a 0-10 scale. We will remind them to mail the nausea assessments back and to state which face represented the maximum nausea after discharge.

Section G: Sample Size/Data Analysis

G1. Sample Size

How many subjects (or specimens, or charts) will be used in this study?

Local: 387 Worldwide: 387

Please indicate why you chose the sample size proposed:

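### Aim 4 seeks the BARF and VAS scores that go with wanting treatment, but the plan offers only a rank correlation for BARF, which yields no score on either scale

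*Combined protocol and SAP*

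**What the plan says.** The background before Section D lists, among the things still unknown about the BARF scale, "the score associated with a patient's perception of a need for treatment". Section D turns this into aim 4, for both scales: "The BARF and VAS scores associated with a patient's perception of the need for treatment".

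F2 collects what the aim needs. Both scales are completed at each in-hospital time point. After the first PACU assessments the children rate the change in their nausea, and "They will also be asked if they want any treatment of their nausea". Drug treatment in the PACU is a separate matter, given "as prescribed by the Attending Anesthesiologist based on his opinion of the clinical needs of the situation".

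G1 asserts adequate power for this aim, again naming both scales: "This sample size will have a >80% power for the other aims of the study (The BARF and VAS scores associated". It gives no test, effect size, request rate or precision target.

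G2 item (4) is the only analysis linked to the aim: "The BARF score and its relationship to the request for rescue antiemetics will be examined by a Spearman's rank correlation". Items (2), (3) and (5) each cover BARF and VAS; item (3), for example, begins "Changes in BARF and VAS nausea scores will be calculated". Item (4) covers BARF alone.

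**The concern.** The aim asks for a quantity in score units, and the planned statistic has no units. Spearman's rho says whether children with higher scores tend to ask for treatment more often. It does not say at what score they do so. The VAS half of the aim has no analysis at all.

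Two further gaps sit in the same item. The outcome is called a request for rescue antiemetics and is never linked to the question that children are asked in the PACU. Each child is also assessed several times, and the item does not say which score is used.

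The data will exist, so a cut-off could be derived later. The outcome, the assessment and the cut-off rule would then be picked after the results are known.

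**Working it through.** **1. Is the score estimated anywhere else in G2?**

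- Item (1): overall mean, SD and distribution of scores, not split by wish for treatment. Its BARF cut-off (>6, severe nausea) is fixed in advance, not derived from wish for treatment.
- Item (2): ability to use the scales, by age.
- Item (3): score changes in children who report a little better or a little worse.
- Item (5): agreement of repeated scores when nausea is unchanged.

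None gives scores by wish for treatment, so aim 4 rests on item (4) alone.

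**2. What does the power statement cover?** The figure of >80% cannot be reproduced, because no inputs are given. For a Spearman test at two-sided 0.05 and 80% power, the smallest detectable rho is tanh[(1.96 + 0.84) × √(1.06/(n − 3))]. At n = 387 this is tanh(2.80 × 0.0525) = 0.15; at n = 279 it is 0.17; at n = 93 it is 0.30. The sample can detect a weak association, which says nothing about how precisely a score is located.

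**3. Does rho carry the location?** Rho depends on ranks only. In a simulated sample, adding 4 points to every score left rho at 0.744, while the best cut-off by Youden's index moved from 3 to 7.

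**4. Illustration on the BARF scale.** G1 supplies one input: "the mean BARF scores in the postoperative period in children was 1.6 +/- 2.4". The rest is assumed: scores of 0, 2, 4, 6, 8 and 10, and a logistic chance of wanting treatment, 1/(1 + exp[−s(x − c)]). Here c is the score at which half want treatment and s is the slope per point. The maximum-entropy distribution with that mean and SD has probabilities 0.575, 0.223, 0.100, 0.051, 0.030 and 0.021. Check: mean = 0.446 + 0.400 + 0.306 + 0.240 + 0.210 = 1.60.

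Rho is the covariance of mid-rank position R and the yes/no answer, divided by the product of their SDs. R is 0.2875, 0.6865, 0.848, 0.9235, 0.964 and 0.9895, with mean 0.5 and SD 0.258. With π the overall share wanting treatment:

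- c = 7, s = 1: π = 0.062; rho = (0.0587 − 0.0312)/(0.258 × √(0.0624 × 0.9376)) = 0.44.
- c = 2, s = 0.5: π = 0.433; rho = (0.2724 − 0.2167)/(0.258 × √(0.433 × 0.567)) = 0.44.

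The correlation is the same, and the 50% points are five scale points apart. Further results:

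| Setting | Rho |
|---|---|
| s = 1, c = 3 / 5 / 7 | 0.67 / 0.58 / 0.44 |
| s = 0.5, c = 2 / 3 / 4 / 5 | 0.44 / 0.45 / 0.46 / 0.45 |

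At a fixed slope of 1, rho does move with c. At slope 0.5 it is nearly flat from 2 to 5, against a sampling SD of about 0.06 at n = 251 (387 × 0.65, using G1's 35% dropout). Solving for rho = 0.40 gives a solution at every whole-number c from 2 to 7, with slopes of 0.42 to 0.53 and request rates from 44% down to 10%. Two other skewed shapes with the same mean and SD (zero-inflated geometric and beta-binomial) gave nearly the same values.

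**5. Would the planned sample support a cut-off?** Same assumptions, n = 251, logistic 50% point:

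| True point | Slope 1: children wanting treatment; 95% half-width | Slope 0.5: children wanting treatment; 95% half-width |
|---|---|---|
| 3 | 65; ±0.5 | 86; ±0.7 |
| 5 | 32; ±0.7 | 49; ±1.1 |
| 7 | 16; ±0.9 | 27; ±1.4 |

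Adjacent BARF faces are taken to be 2 points apart, so the BARF estimate would be usable across this range.

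**The case against.** Aim 4 speaks of associated scores and does not use the word threshold. The least that would answer it is a summary of BARF and VAS scores by wish for treatment; an ROC or logistic cut-off goes further. This is fair as to wording, although the background speaks of a single score. The weaker reading does not rescue the plan, since no such summary is planned and the VAS is missing on any reading.

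The PACU question is the only place where a child's wish is recorded, so it is the natural source for the request in item (4), and the plan does not propose to use drug records instead. That stands: one clarifying phrase settles it.

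Some illustrative cases are strained. With c = 2 and s = 0.5, 27% of children with no nausea would want treatment (1/(1 + e) = 0.27), and so would 43% overall, above the 33% PONV incidence assumed in G1. In the rho = 0.40 example, points 2 and 3 imply 44% and 36%. Only points 4 to 7, at 29% down to 10%, stay below 33%. The collected data would also show the request rate, which narrows the ambiguity. That stands too, but the argument does not depend on the simulation.

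Finally, this is a minimal-risk observational study, the gap touches one of five aims, and design, sample and safety are unaffected. That bears on urgency, not on whether the defect exists.

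**Conclusion.** The concern holds. Carried out exactly as written, the plan yields an association for BARF, nothing for VAS, and no treatment-related score on either scale. Aim 4 is therefore only partly addressed for BARF and not addressed for VAS. This follows from the text and needs no assumption.

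The size of the ambiguity does rest on assumptions: the BARF scoring, the logistic form and the score distributions fitted to the quoted mean and SD. Under them, a rho of 0.40 leaves the 50% point anywhere from 2 to 7, or from 4 to 7 if the request rate is held below 33%. The precision figures are for BARF only; none was worked out for VAS.

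Item (4) should be corrected before analysis, because it cannot deliver its aim. The consequences are confined to that aim, and the data to repair it are already being collected.

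**What to change.** Rewrite G2 item (4) for both BARF and VAS:

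- **Outcome.** Use the child's PACU answer on wanting treatment, coded yes/no, and state how the request for rescue antiemetics relates to it.
- **Description.** Report the distribution of each score by that answer, with the number and share of children who want treatment.
- **Estimate.** Give a cut-off for each scale with a 95% CI, either from an ROC analysis (sensitivity and specificity at each BARF face and across the VAS) or from logistic regression.
- **Rule.** Name the cut-off rule in advance, because rules can disagree. In simulation with a true 50% point of 7 and slope 0.5, Youden's index chose 4 in about 72% of samples.
- **Unit of analysis.** Use one prespecified PACU assessment per child, or account for clustering by child.
- **Power.** In G1, replace the general power claim for this aim with the expected precision of the cut-off over a stated range of request rates.

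Spearman's correlation may stay as a descriptive extra. A paired comparison of the two scales' ROC areas is optional.

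The cost is a few sentences and slightly more analysis, with no new data or subjects. The drawback is a wide interval if few children want treatment; the documents give no request rate, so this cannot be settled in advance.
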